Elderly with T2D have higher risk of developing dementia, MCI, and cognitive decline. T2D is a vascular disease culminating in tissue hypoxia, so cerebrovascular disease is the primary contributor to this increased risk. Impairment of cerebrovascular integrity in T2D may lead to reduced CBF on the vessel level, and reduced glucose metabolism on the neuronal level, which may be rectified with HBOT by cerebral vascular repair processes. We thus propose a randomized controlled trial (RCT) of the beneficial effects of HBOT on cognition and on ischemic injury (through assessment of CBF using MRI, and of glucose metabolism using FDG-PET). We focus on T2D elderly with MCI, who are enriched in cerebrovascular disease and are in the prodromal phase of the dementia process, an ideal opportunity for HBOT to protect and enhance cognition by reversing, preventing, or delaying neuropathologic processes that cause cognitive decline. We will test the extent to which 60 sessions of 90 minutes of 100% oxygen at 2 ATA—compared with a sham condition—improve cognitive performance in the short term (immediately after treatment) and a longer term (12 months after treatment). Subjects will be recruited through talks in the community, advertisements, and companies which have large lists of elderly interested in receiving emails about health related topics. In addition, we have a large-scale project in Israel (NIA R01AG034087), where 1200 T2D elderly are followed for cognitive decline providing an additional large recruitment source.

We hypothesize that HBOT compared to a sham condition (n=77 in each group) improves cognitive function and favorably alters cerebrovascular pathology (increasing CBF and glucose utilization) in T2D patients with MCI, focusing on the following outcomes:

Aim 1. Cognitive functioning: Aim 1a: *The primary outcome will be a composite measure of cognitive function balancing tests of both executive and memory function. Domain-specific measures of cognition (executive function and episodic memory) will be secondary outcomes.*

Aim 2. Ischemic Injury: CBF at the level of capillaries in gray matter measured by MRI arterial spin labeling, and in macrovessels, measured by a novel 4D Flow MRI technology developed by our group.

Aim 3. Neuronal function: [F18]FDG-PET measuring cerebral glucose utilization.

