B2. The primary underlying mechanism for HBOT benefits on cognition is cerebrovascular- HBOT is a treatment in which oxygen-enriched air (up to 100%) is administered to patients in a chamber at a pressure above one atmosphere absolute (1ATA), which is the ambient atmospheric pressure. For the peripheral vasculature, a well-accepted indication of HBOT is hypoxia-induced foot ulcers; there is broad evidence suggesting significant improvements through stimulation of vessel repair processes and angiogenesis^{8, 9}. Similarly, in the brain, based on current evidence in 1) animals, 2) small clinical trials in humans, and 3) our own stroke clinical trial (see D1a), the combined action of hyperoxia and hyperbaric pressure of HBOT improves hypoxia/ischemic injury and consequently cerebral blood flow (CBF) leading to cognitive improvements^{10, 11}. Angiogenesis is induced by HBOT through downregulation of hypoxia-inducible factor-1 α (HIF-1 α)^{12, 13} including in the hippocampus^{14, 15}. HBOT also increases vascular density in the hippocampus, improves spatial learning in rodents¹⁶, reduces cortical infarct area¹⁷ and improves CBF in the piriform cortex of adult rats with vascular dementia¹⁸. Small HBOT studies performed on humans also support our hypotheses¹⁹ and proposed mechanism of action. In a randomized clinical trial (RCT), HBOT treatment as an adjuvant to donepezil showed improved cognitive performance compared with donepezil alone in vascular dementia patients²⁰. Similarly, HBOT had positive effects compared to hyperbaric air on neurological and cognitive outcomes in a small (n=26) controlled trial of patients with cerebrovascular disease (patients, but not investigators, were blind to the study condition)²¹. More recently, HBOT—compared with normobaric oxygen—was associated with increased CBF in frontal and temporal regions in healthy subjects²². Finally, our clinical trial on post-stroke patients showed enhanced CBF and cognition following HBOT. On the neuronal level, it is well established that glucose utilization is impaired in ischemic cortical regions²³⁻²⁵. In animal models there is growing evidence for improved neuronal hypometabolism with HBOT²⁶⁻²⁸, suggesting that intracellular bioavailability of oxygen attenuates the deleterious effects of ischemia on neuronal glucose utilization²⁹. The evidence thus supports investigation of CBF (using MRI) and glucose utilization (using FDG-PET) as biomarker outcomes of HBOT in T2D patients, who are enriched in cerebrovascular disease.

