Aims 2a and 2b: CBF and cerebral glucose utilization will be analyzed with a similar strategy to Aims 1a and 1b except that there will be no 6 month assessment. Mixed effects ANCOVA models will be used to compare changes in these outcome measures from baseline to 12 weeks following treatment, and, as exploratory analyses, linear mixed effects models will be used to assess relationships between treatment group (fixed effect) and the longitudinal trend (random intercept and slope for each subject) in MRI-ASL and FDG-PET outcome measures, assessed at 12-weeks and 12 months following treatment. Vascular effects of HBOT vs. Sham: Since CBF derived from ASL perfusion may represent combined effects of neural metabolism and vascular effects, a secondary mixed effects ANCOVA model (similar to Aim 2b) of vascular changes from baseline to 12 weeks as measured by ASL CBF will adjust for neural metabolism derived from FDG-PET.

Aim 3: Outcome measures (changes in CBF and cerebral glucose utilization) identified as having significant associations with treatment group in Aims 2a and 2b will be further explored as mediators of the relationship between treatment group and the change in cognition. To ensure that measurement of mediator

variables precedes measurement of cognition, we will define the outcome as the change in cognition from baseline to 12 months, and the mediators as changes in CBF and cerebral glucose utilization, from baseline to 12 weeks. The product of coefficients approach will be used within a multiple mediator modeling framework to provide point estimates of both the specific indirect effect (i.e. the effect of treatment group on the change in cognition from baseline to 12 months via a mediator among other mediators in the model) and the total indirect effect (i.e. the sum of specific indirect effects for all mediators in the model). The bootstrapping method⁹³ will be used in each multiple mediator model to compute bias-corrected standard errors (and 95% confidence intervals) for the specific and total indirect effect point estimates.

D7. Power Analysis and sample size justification

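### The mediation model names no baseline adjustment, so shared causes of biomarker and cognitive change, or correlated baselines, can pass for mediation; the specific indirect effects also need a stated interpretation.

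*Combined protocol and SAP*

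**What the plan says.** The last analysis paragraph of Section D6 takes forward only biomarkers "identified as having significant associations with treatment group in Aims 2a and 2b". It sets the outcome as cognitive change to 12 months and "the mediators as changes in CBF and cerebral glucose utilization, from baseline to 12 weeks". By the product of coefficients it estimates a specific indirect effect for each biomarker, defined as "the effect of treatment group on the change in cognition from baseline to 12 months via a mediator among other mediators in the model", and a total indirect effect, "the sum of specific indirect effects for all mediators in the model", with bootstrap intervals. It names neither covariates nor a path from one biomarker to the other.

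Covariates appear in three other places. The Aim 1 and 2 models include the outcome's own baseline value. Under Aims 1a and 1b, D6 lists potential confounders (including age, education, HbA1c, atrophy and white matter hyperintensities), to be added only if they pass a screen of p<0.1 for imbalance or p<0.15 for association. Section D2j uses white matter hyperintensities as covariates in the second-level imaging analysis. None of these is extended to the mediation model.

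On how the two biomarkers relate, the documents say three different things:
- Aims page: "Impairment of cerebrovascular integrity in T2D may lead to reduced CBF on the vessel level, and reduced glucose metabolism on the neuronal level". One vascular cause lies behind both.
- Section B2: "intracellular bioavailability of oxygen attenuates the deleterious effects of ischemia on neuronal glucose utilization". Oxygen supply acts on metabolism.
- Section D6, Aims 2a and 2b: "Since CBF derived from ASL perfusion may represent combined effects of neural metabolism and vascular effects". Metabolism contributes to measured flow.

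**The concern.** A product-of-coefficients estimate multiplies the effect of treatment on the biomarker (a) by the association of the biomarker with cognition given treatment (b). Randomisation identifies a. It does nothing for b, because participants whose CBF or glucose uptake improves more may differ from the rest in ways that also affect cognition. Measuring the biomarker before the outcome deals with reverse timing, not with common causes. Change scores remove stable differences between people, but they remain negatively correlated with their own baseline. If baseline biomarker and baseline cognition are correlated, the two changes are correlated as well, with no causal link between them.

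If treatment moves a biomarker and b is spurious, the trial reports a mechanism that does not exist. Sections C4 and D8 intend to use what this pilot learns to design a multi-centre trial, so a false mechanism would carry forward.

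The second issue is interpretation. The specific effect of CBF holds FDG constant, and the reverse. If one biomarker acts partly through the other, the upstream one is credited only with the part that bypasses the downstream one.

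**Working it through.** **The plan's own figures.** Section D7, Table 3: CBF 2.73/5.6 = 0.4875; glucose utilisation 2.145/4.40 = 0.4875; stated effect size 0.49. Noncentral-t power at 67 per arm, two-sided 5%, is 0.800 for both, as the plan says. Allowing for dropout, 67/0.87 = 77.01, against 77 enrolled. The evaluable number used below is 2 × 67 = 134. The mediation analysis has no power or effect figure of its own, and the documents give no correlation between biomarker change and cognitive change. All path values below are therefore assumptions.

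**False mediation, by hand.** Suppose treatment moves one biomarker by the planned amount (80% chance of significance) and the biomarker has no effect on cognition. Mediation is declared when both a and b are significant. If the two changes have within-arm correlation q, the b test has 134 − 3 = 131 degrees of freedom, noncentrality δ = q√131/√(1 − q²) and critical value 1.978. The false-declaration rate is about 0.80 × P(b significant).

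The correlation q arises as follows:
- A common cause correlated r with each change gives q = r².
- After adjustment for a proxy correlated 0.5 with that cause, q = 0.75r²/(1 − 0.25r²).
- With baselines correlated ρ and each measure correlated s with its own follow-up, each change has variance 2(1 − s) and their covariance is (1 − s)²ρ, so q = ρ(1 − s)/2.

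| Situation (assumed) | q | δ | P(b significant) | × 0.80 | Simulated |
|---|---|---|---|---|---|
| None, or cause fully adjusted | 0 | 0 | 0.05 | 4% | about 4% |
| Common cause, r = 0.3 | 0.09 | 1.03 | 0.18 | 14% | 15% |
| Common cause, r = 0.4 | 0.16 | 1.86 | 0.45 | 36% | 36% |
| r = 0.3, proxy adjusted | 0.069 | 0.79 | 0.12 | 10% | 10% |
| r = 0.4, proxy adjusted | 0.125 | 1.44 | 0.30 | 24% | 24% |
| Baselines only, ρ = 0.5, s = 0.8 | 0.05 | 0.57 | 0.09 | 7% | 7% (low end) |
| Baselines only, ρ = 0.6, s = 0.5 | 0.15 | 1.74 | 0.41 | 33% | 32% (high end) |

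The simulations used 4,000 trials of 134 participants. For the baseline rows, the simulated range was 7% to 32%, and about 4% once baseline cognition and baseline biomarker were in the model. The ρ and s shown are examples that reproduce the two ends. In effect-size terms, a common cause with paths of 0.3 gives a spurious indirect effect of 0.49 × 0.3² = 0.044 SD; with paths of 0.5 it is 0.49 × 0.5² = 0.12 SD.

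**Order of the biomarkers.** These are large-sample linear models with a CBF effect of 0.49, a CBF-to-FDG path of 0.5 and an FDG-to-cognition path of 0.5, all assumed except the first.
- Pure chain (CBF to FDG to cognition): specific CBF 0.000, specific FDG 0.122, total 0.122. The true effect through CBF is 0.49 × 0.5 × 0.5 = 0.123.
- With a direct CBF-to-cognition path of 0.25 added: specific CBF 0.123, against 0.245 truly passing through CBF.
- Pure chain, FDG measured with error SD 0.5 or 1.0: specific CBF 0.031 or 0.070.
- Reverse chain (metabolism to CBF to cognition): specific FDG 0.000, specific CBF 0.122.

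In each case the total indirect effect equals the true effect through the biomarkers. Entry to the model matters too. In the pure chain FDG has effect size 0.49 × 0.5 = 0.245, so at 67 per arm both biomarkers enter in 27% of trials and CBF enters alone in 53%, in which case it carries the whole effect. What the CBF effect means therefore depends on whether FDG passed a significance test.

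**The case against.** A reader might infer something stronger: that the plan says flow drives metabolism, so the CBF-specific effect vanishes exactly when the plan's mechanism is true and the trial would then report that blood flow is not a mechanism. The documents do not support that. Section B2 points from oxygen supply to metabolism, but the aims page gives a common cause and D6 gives the reverse direction. A zero needs CBF to act only through FDG, FDG to be free of error, and both biomarkers to enter; the plan asserts none of these. A pure chain with a path of 0.5 also conflicts with Table 3, which assumes 0.49 for FDG rather than 0.245. If FDG does reach 0.49 with that path, half its effect bypasses CBF; both biomarkers then enter in about 68% of trials, and the specific CBF effect is still near zero. Above all, the Aim 4 hypothesis is joint, and the planned total indirect effect answers it whatever the order. Declining to impose an order is defensible.

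On confounding, three objections have weight. The covariate rule might have been meant to carry over, so the accurate description is that adjustment is not specified. The fall to 4% assumes the common cause is measured; with a proxy correlated 0.5 the rates fall only to 10% and 24%, and nothing shows that the listed baseline variables cause change. The calculation uses joint significance, not the planned bootstrap. Finally, the analysis is exploratory, in a pilot, and no primary conclusion rests on it.

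These points limit the size of the problem but do not remove it. Even if the D6 rule carried over, adjustment would depend on p-value screens, and baseline biomarker values are not on its list. The total indirect effect is robust to order but not to confounding.

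**Conclusion.** The point holds for adjustment. As written, the mediation model leaves the biomarker-to-cognition path exposed to common causes of change and to correlated baselines. False declarations of 7% to 36%, against about 4% with full adjustment, illustrate the possible scale at 134 participants. They are not a forecast: they rest on assumed correlations, a joint-significance test and a treatment effect on the biomarker of the planned size. With weakly correlated baselines and no common cause the inflation would be small. Adjustment removes the baseline artefact, but an imperfectly measured common cause only in part.

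The ordering point is secondary and concerns interpretation. Each specific effect can understate an upstream biomarker, by half in the partial-chain example and to near zero only in a pure chain with both biomarkers in the model. It does not follow that the plan would dismiss blood flow as a mechanism, nor that a flow-first split should replace the specific effects.

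**What to change.** In the mediation paragraph of Section D6:

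1. Adjust the mediator and outcome equations, without p-value screening, for baseline cognition, baseline CBF and FDG, age, education, HbA1c and baseline white matter hyperintensities.
2. Add a sensitivity analysis showing how strong an unmeasured common cause of biomarker and cognitive change would have to be to remove the indirect effect.
3. Base the Aim 4 conclusion on the total indirect effect, which is already planned.
4. Keep the specific effects, stating that each is the part not passing through the other biomarker in the model, and report which biomarkers entered.
5. Show ordered decompositions in both directions (CBF first, FDG first) as sensitivity analyses only, because both are measured over the same 12 weeks and the documents do not settle the order.

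All these variables are already collected, so no new visits or measurements are needed. The cost is wording, a few degrees of freedom and a little more analysis. The analysis stays exploratory, and any split between the two biomarkers still depends on an assumed order, which has to be stated.

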D2c. Procedures- **Table 2** presents study procedures for each subject. HBOT sessions will take place in Asaf Harofeh Medical Center; informed consent and all other assessments, including cognitive, functional, MRI, and FDG-PET will be performed at the Sheba Medical Center. Adverse event monitoring is done at every HBOT and sham session, by a nurse in the chamber throughout the session and a physician always present. Physical exams and blood collection for safety monitoring will occur before randomization, and at 12 weeks. Medication review will occur before randomization, before and after the intervention, and 6 and 12 months later, with cognitive testing at these times except before randomization. The T2D-related biomarkers (Blood test, MRI ASL and FDG-PET) will be assessed before and after the intervention, and 12 months later. After intervention, a questionnaire will examine whether blindness was maintained. At the end of the participant's 12 months' participation in the trial, the participant can choose to receive HBOT treatment for which the costs will be covered by the study team. At the end of the second HBOT treatment course, an additional neuropsychological assessment will be administered to the participants.

D2d. Randomization and Blinding of Intervention-Eligible candidates will be randomized with equal probability to the HBOT and sham interventions. When a cluster of at least 3 subjects from one of the interventions is filled, the intervention for that cluster will begin (77 subjects will be recruited for each treatment). Clusters will be a random effect in the analyses (see D6). Three study technicians who activate HBOT or sham protocol sessions will be the only unblinded staff who have the key for the subjects' group assignments. All subjects and other clinic staff will remain blinded to group assignment. Study nurses will monitor AEs during all sessions and a physician will be present during each session. Importantly, staff from Sheba, who assesses outcomes, will not be exposed to the subjects during their intervention and vice-versa.

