Procedures before enrollment will maximize participant adherence to the intervention. Only volunteers who fully understand the expectations regarding consistent participation in the treatment and completion of assessments will be enrolled. The judgment of field site staff will be essential to determine eligibility based on anticipated adherence. During initial telephone screening and again prior to the baseline visit, subjects will be asked to confirm their willingness to be assigned to either intervention. [name] group has long experience with RCTs using HBOT conditions, ensuring subject satisfaction and continued commitment to the program.

D2e. HBOT intervention- The multiplace HBOT unit at Asaf Harofeh is state of the art, the most advanced available in the market. The inside looks like an airplane, with comfortable chairs for 11 subjects and the nurse who stays throughout the session (a significant advantage compared to the monoplace chamber). The HBOT protocol is 90 minutes, 5 times/week, 60 sessions, 100% oxygen at 2 ATA with 5 minute air breaks every 30 minutes. This safe protocol is used worldwide for treatment of ischemic non-healing wounds (diabetic foot or post radiation injury), was used in our stroke clinical trial⁷⁸, and in our MCI preliminary data, indicating favorable cognitive outcomes. It improves on a prior study on memory-impaired elderly⁸⁹ that was too short to reduce ischemic injury or for angiogenic processes to occur, even in peripheral tissue⁹⁰⁻⁹².

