D6. Statistical Analysis Plan- Efficacy analyses will be performed for the intent-to-treat (ITT) population, our primary analysis, and for fully and partially compliant per-protocol (PP) populations. The ITT population will include all participants in the group to which they were randomized, regardless of any protocol deviation including non-compliance, adverse events, or loss of follow-up. The PP populations will include participants in the group according to the intervention actually received, but a separate analysis will be performed for those who were fully compliant (at least 80% of sessions completed) and for those who were partially compliant (at least one session completed). A complier-average causal effect (CACE) analysis using a latent class modeling approach will also be performed on both fully and partially compliant populations. Patients missing a baseline value of a continuous efficacy outcome measure will be excluded from all analyses and maximum likelihood estimation methods will be used to handle missing data arising from an unobserved follow-up visit¹²².

Aims 1a and 1b: The primary (overall cognition) and secondary (executive functions, episodic memory domains, and computer-based tests) cognitive outcome measures (all summaries of z-scores), will each be analyzed using a mixed model analysis of covariance (ANCOVA) with time of assessment (baseline or 12 weeks) as the within-subjects factor, treatment group (HBOT vs. sham) as the between-subjects factor and baseline value of the outcome measure as the covariate. *Both, subject and 'cluster' (the variable used to identify to which group of at least 3 subjects each individual is assigned) will be modeled as random effects to account for the correlation among repeated measurements made over time within a subject as well as potential 'cluster effects' arising from blocks of at least 3 patients receiving treatment at a particular time after randomization.* An interaction term between time of assessment and treatment group will be included in each model allowing for estimation of the mean change from baseline to 12 weeks in each treatment group as well as a test for difference

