in change scores between groups. A test of parallel treatment effects across the range of baseline values will be conducted by including a three-way interaction term among time of assessment, treatment group and baseline value of the outcome variable as well as all lower order two-way interaction terms. If the three-way interaction term is statistically significant it will be retained in the final model and estimates of the difference in mean change scores between treatment groups will be evaluated at selected percentiles of the baseline distribution. Secondary mixed model ANCOVA analyses will be performed for cognitive assessments at 6 and 12 months following treatment. As an exploratory analysis, linear mixed effects models will assess the relationship between treatment group (fixed effect) and the longitudinal trend (random intercept and slope for each subject) in the primary and secondary cognitive outcome measures, assessed at 12-weeks, 6 months and 12 months following treatment. The primary hypothesis will be tested by assessing the interaction between treatment group and time of cognitive follow-up assessment, with a significant interaction indicating a difference in longitudinal cognitive trends between treatment groups. Potential confounders (age, gender, education, *duration of T2D, HbA1c, diabetes medications [insulin vs. no medications and oral agents vs. no medication], levels of atrophy and white matter hyperintensities*) will be included as covariates if there is imbalance at baseline ($p<0.1$) or association between the covariate and the response ($p<0.15$).

To explore whether specific dichotomized T2D characteristics (such as the last HbA1c level (dichotomized at 7) in the Diabetes Registry, the number of T2D complications, and the number of severe hypoglycemic episodes in the year preceding randomization) are associated with greater improvements following treatment with HBOT, mixed effects ANCOVA models similar to those for Aims 1 and 2 will add a main effect for the specific T2D characteristic and an interaction term between treatment group and the characteristic. Using the MHS dataset, we will also explore associations of dosage of the most prevalently used medications with cognitive outcomes. When potential confounders are associated with cognitive outcomes, this also may identify subgroups for which HBOT is particularly effective.

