Aim 1. Power is presented for detecting the difference in mean change (from baseline to 12 weeks) in overall cognition z-scores between the sham and HBOT treatment groups. Power calculations are based on two-sample t-tests and are conducted with a 2-sided 5% significance level (**Table 3**). A 2-sample t-test provides a more conservative power estimate than the proposed mixed model approach, which is expected to explain more variability and thus have more power to detect the same effect size with the same sample size.

The predicted mean change in the sham group from baseline to 12 weeks is -0.02 (based on the IDCD 12-week change in overall cognition). Assuming an SD of 0.50 in both the sham and HBOT groups, with a minimum sample size of 67 patients per arm, we have 80% power to detect an improvement in the HBOT group of 0.224, a “medium” effect size of 0.49. To account for an anticipated dropout rate of 13% (a reasonable estimate compared to the 5% dropout rate in our stroke study), we plan to enroll 77 patients per group for a total of 154 patients. Our HBOT trial years after mild traumatic brain injury⁷⁴ had an effect size of 0.47 for information speed processing which is clinically comparable to our primary outcome measure of overall cognition, and our HBOT trial on stroke patients⁷⁸ showed an effect size of 0.49 for the National Institutes of Health stroke scale, suggesting our detectable effect size of 0.49 is feasible.

Aim 2: As for Aim 1, power is presented for detecting the difference in the mean changes in CBF velocity and cerebral glucose utilization between the Sham and HBOT groups. Assuming a mean change in CBF velocity of -0.45 in the Sham group and an SD of 5.6 in both groups, with a minimum sample size of 67 patients per arm we have 80% power to detect an improvement in the HBOT group of 2.28, an effect size of 0.49. *To account for an anticipated dropout rate of 13%, we plan to enroll 77 patients per group for a total of 154 patients.* For cerebral glucose utilization, assuming a mean change in the sham group of -0.08 and an SD of 4.40 in both groups, with

Table 3: Two group t-test of equal means, equal n's)*			
	Outcome		
	Overall Cognition z-score	CBFV [†]	CGU [‡]
Sham Mean Change, D ₁	-0.020	-0.450	-0.08
HBOT Mean Change, D ₂	0.224	2.28	2.065
Difference in means, D ₁ -D ₂	-0.244	-2.73	-2.145
HBOT SD	0.50	5.60	4.40
Minimum N per group	67	67	67
Enrollment N per group**	77	77	77

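### D7 calls its t-test power conservative, but it applies no design effect for the single-arm treatment clusters and relies on a precision gain that the D6 model, read literally, does not give

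*Combined protocol and SAP*

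**What the plan says.** D7 bases power for all three outcomes in Table 3 on a two-sample t-test of change from baseline to 12 weeks (two-sided 5%, 67 per arm, 80% power). It inflates only for 13% dropout, to 77 per arm. It then says: "A 2-sample t-test provides a more conservative power estimate than the proposed mixed model approach". The one reason given is that the model should explain more variability.

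D2d describes how treatment starts: "When a cluster of at least 3 subjects from one of the interventions is filled, the intervention for that cluster will begin". Each cluster therefore belongs to one arm. D2e describes the chamber as having "comfortable chairs for 11 subjects and the nurse who stays throughout the session".

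D6 gives subject and cluster random effects, the latter for possible effects "arising from blocks of at least 3 patients receiving treatment at a particular time after randomization". The primary model is set up "with time of assessment (baseline or 12 weeks) as the within-subjects factor", with "baseline value of the outcome measure as the covariate", and the treatment effect is the time-by-group interaction. A three-way interaction of time, group and baseline is tested together with its lower-order terms: "If the three-way interaction term is statistically significant it will be retained in the final model". What stays in the model otherwise is not said. For dropouts, "maximum likelihood estimation methods will be used to handle missing data arising from an unobserved follow-up visit". CBF and glucose utilization follow a similar strategy.

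**The concern.** D6 treats cluster effects as a real possibility, while D7 leaves them out and still calls its figure conservative. Clusters nested in arm add between-cluster variance to the treatment contrast, so a positive ICC lowers power unless something offsets it.

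The offset D7 relies on is the mixed model's explained variability. In D6, however, the baseline score is both a level of the repeated outcome and a covariate. A covariate that is constant within a subject cannot reduce the variance of that subject's change.

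Two things are at stake: the 80% that justifies 67 and 77 per arm for three outcomes, and, on the literal reading, the 5% level of the primary test.

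**Working it through.** **Inputs from D7 and Table 3.** Cognition: difference 0.224 − (−0.020) = 0.244, SD 0.50, d = 0.488. CBF: 2.73/5.60 = 0.4875. Glucose: 2.145/4.40 = 0.4875. n = 67 per arm, two-sided 5%.

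**Assumptions.** The documents give neither an ICC nor a baseline-to-follow-up correlation r. I use ICC 0.01 to 0.10 and r = 0.5, 0.7 and 0.8.

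**1. The plan's own figure.** Noncentral t with 132 df and noncentrality d√(n/2) gives 80.06% for cognition and 79.98% for CBF and glucose. Dropout: 67/0.87 = 77.01. The figures reproduce, with no slack.

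**2. Clustering, valid test of change.** Design effect DE = 1 + (m − 1)·ICC; noncentrality d√(n/(2·DE)). Subject df = 132; cluster df = 2(67/m − 1), which is 42.7 at m = 3. Power for cognition:

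| Cluster size m, df basis | ICC 0.01 | 0.02 | 0.05 | 0.10 |
|---|---|---|---|---|
| 3, subject df | 79.3% | 78.5% | 76.2% | 72.6% |
| 3, cluster df | 78.0% | 77.2% | 74.9% | 71.2% |
| 5, subject df | 78.5% | 77.0% | 72.6% | 65.9% |
| 11, subject df | 76.2% | 72.6% | 62.9% | 50.9% |

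For CBF and glucose at m = 3: 79.2/78.4/76.1/72.5% (subject df) and 77.9/77.2/74.8/71.1% (cluster df).

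Eleven is only the number of seats. D4 expects about 47 subjects a year, or 23.5 per arm, so three in one arm take about 3/23.5 × 52 = 6.6 weeks and eleven about 24 weeks. The Table 2 footnote has treatment starting within three weeks of baseline. Clusters near 3 are therefore the realistic case.

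**3. The D6 contrast read literally.** The model is outcome ~ time × group + baseline, with random subject and cluster intercepts. With complete data, baseline is the same at both visits and cancels from the time-by-group contrast. So does a cluster intercept common to both visits. In simulated trials the estimate equalled the raw difference in mean change to about 1e-15. The true sampling variance is therefore that of the change-score comparison.

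The reported standard error is nevertheless smaller. With equal variances σ² at both visits, the pooled slope on baseline is (1 + r)/2. The residual variances are σ²(1 − r)²/4 at baseline and σ²[(1 − r²) + (1 − r)²/4] at 12 weeks. The two residuals are negatively correlated, so the subject variance is estimated at zero in most runs. The average residual variance is σ²(1 − r)(3 + r)/4, which makes the model's SE √((3 + r)/4) of the t-test SE: 0.935, 0.962 and 0.975 at r = 0.5, 0.7 and 0.8. At r = 0.5 the SEs are 0.081 and 0.086. This is an understated SE, not a gain in precision.

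Type I error in simulation (REML, 22 clusters of 3 per arm, cluster effect arising at 12 weeks, ICC of the change score, 20,000 runs per cell, 130 df):

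| r | ICC 0 | 0.01 | 0.02 | 0.05 | 0.10 |
|---|---|---|---|---|---|
| 0.5 | 6.5% | 7.1% | 7.3% | 8.2% | 9.7% |
| 0.7 | 6.0% | 6.0% | 6.3% | 7.5% | 9.2% |
| 0.8 | 5.9% | 6.1% | 6.3% | 7.1% | 8.7% |

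Nominal rejection at a difference of 0.244 is about 80% to 84%, but a test that exceeds its level cannot claim that as power. For comparison, a change-score t-test that ignores clusters of 3 gave 5.2%, 6.0% and 7.7% at ICC 0.02, 0.05 and 0.10. The literal model adds the understated SE to that.

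Dropout was approximated separately by least squares without a cluster term (78 per arm at baseline in 26 clusters of 3, 67 followed at random, 4,000 runs, r = 0.5 and 0.8, ICC 0, 0.05 and 0.10). Type I error was 7.8% to 11.0% and nominal rejection 82.5% to 86.8%.

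**4. If the 12-week score adjusted for baseline is meant.** With equal variances, the effect size becomes d/√((1 + r)/2). Clusters of 3, cluster df, ICC of the adjusted score:

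| r | ICC 0.01 | 0.02 | 0.05 | 0.10 |
|---|---|---|---|---|
| 0.5 | 88.4% | 87.8% | 86.0% | 82.9% |
| 0.7 | 84.2% | 83.5% | 81.5% | 78.0% |
| 0.8 | 82.1% | 81.4% | 79.2% | 75.7% |

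Nine of 12 cells reach 80%. Ignoring the loss of df, the gain outweighs clustering while DE < 2/(1 + r). At m = 3 that means an ICC below 0.167, 0.088 and 0.056 for r = 0.5, 0.7 and 0.8.

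**The case against.** No figure in D7 or Table 3 is miscalculated. At clusters of 3 and an ICC of 0.02 or less, the loss is under two points with subject df. The 11-seat results are remote. All of this stands.

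The strongest argument is that an ANCOVA with baseline as covariate normally means the follow-up score adjusted for baseline. D6 does fit time-by-baseline when it tests the three-way term, and it never says that the term is then dropped. On that reading D7's sentence is true over most of the assumed range. With subject df, 10 of 12 cells reach 80% (80.5% at r = 0.8, ICC 0.05; 79.3% at r = 0.7, ICC 0.10). Other prognostic covariates listed in D6 could add a little. But the sentence then holds only under conditions that D7 does not state and for a model that D6 does not clearly define. On the literal reading, covariates entered as main effects cancel as well.

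D2a also mentions 250 participants, against 154 in D7. At 125 per arm and 13% dropout (about 109 evaluable), change-score power with clusters of 3 would be about 90% to 94% over the same ICCs. The documents do not reconcile the two totals, and D7's justification rests on 154. A larger trial would restore power but would not correct the literal model's error rate.

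**Conclusion.** The concern holds. The t-test arithmetic is right for independent subjects; the statement that it is conservative is not supported. Whether true power is above or below 80% depends on cluster size, ICC, baseline-to-follow-up correlation and the model intended, and D7 states none of the first three while D6 leaves the fourth open.

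At the realistic cluster size of 3, a valid test of change loses roughly 1 to 9 points over ICC 0.01 to 0.10, across both df bases. A properly specified baseline-adjusted analysis recovers this in most scenarios, but not all.

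The D6 wording is the more serious part: followed literally, the nominal 5% test runs at about 6% to 10% with complete data. The treatment estimate itself is not biased with complete data. All ICCs and correlations here are assumptions. This should be corrected; it does not invalidate the design.

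**What to change.** **D6.** Define the primary model as the 12-week score with baseline as covariate and a random cluster effect. Alternatively, keep the repeated-measures form and add time-by-baseline and cluster-by-time terms. Say which terms remain when the three-way interaction is not significant, and name the degrees-of-freedom method.

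**D7.** Delete or qualify the sentence on conservatism. Restate power for all three Table 3 outcomes as a sensitivity table over expected cluster size, an assumed ICC range and an assumed baseline-to-follow-up correlation, without presenting any one ICC as established. Suggested text: *The 80% figure assumes independent subjects. Because treatment is delivered in clusters of at least 3, power is also shown over a range of assumed ICCs, cluster sizes and baseline-to-follow-up correlations.*

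**Cost.** Changes to text and Table 3 only, with no extra patients. The stated power becomes conditional and may fall slightly below 80% in part of the range.
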